i. Whether you will include a witness to the consent process and why:

N/A

j. If the language is unwritten, explain how you will communicate accurate information to potential participants and whether you will use props or audio materials:

N/A

2. Identify the countries where the research will take place, and the languages that will be used for the consent process.

Table 3. Country and Languages for Consent

Country	Consent Document(s) (Adult Consent, Parental Permission, Youth Assent, etc.)	Languages
U.S.A	Adult Consent Documents, Parental Permission, Youth Assent	English

C. Study Implementation:

IRB #00020570 +CiM/HSP research plan v7 14Nov2022

Pls: [name] (Faculty PI) & [name] (Navajo Community PI)

1. Describe the procedures that participants will undergo. If complex, insert a table below to help the reviewer navigate.

Following consent/assent and screening, participants will be block randomized (with blocking on age [e.g., caregiver vs. youth] and gender) by REDCap into either the comparison group (coping plan with two follow-up check-ins) or the intervention group (coping plan with two follow-up check-ins and culturally adapted Caring Contacts). All participants, regardless of group, will receive up three COVID-19 safety text messages/postcards. These messages will be sent at approximately 45-, 60-, and 75-days post-enrollment and cover the following topics: respect and protection for others during the ongoing pandemic, compassion towards others by wearing a mask if necessary and getting tested if appropriate and protecting yourself and others by staying up to date on vaccination and boosters. See Table 4 for a summary of intervention activities by group.

Table 4. Intervention activities by study group

Tuble 4: Intervention detivities by study group												
Intervention Activities	M1		M2			M3						
	Q1	Q2	Q3	Q4	Q1	Q2	Q3	Q4	Q1	Q2	Q3	Q4
All Participants (est. N = 137)												
Coping Plan Intervention	Χ											
Follow-up check ins	Χ	Χ										
COVID-19 Prevention Messages							Χ		Χ		Χ	
Caring Contacts participants (est. N = 69)												
Caring messages			Χ	Χ	Χ	Χ		Χ		Χ		Χ

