i. All Participants: Coping Plan, follow-up check-ins, and COVID-19 messages est. *N* = 137 All study participants will receive a one-hour support visit (either by phone or in-person) from a study staff person to develop an individualized plan for coping with life's challenges. This modified safety plan will include information on who and where they can get help during tough times or when they are feeling down. It will also include some ways they can work through these challenges. The plan is an adapted version of the evidence-based Safety Planning Intervention (described in background section) and was designed to address the underlying risk of suicide and other mental health stress as well. A couple of days after this visit, a study staff person will call the participant to check-in on how things are going and make additional community referrals. A second check-in will occur the following week. All staff will receive additional training on completing a coping plan. Finally, all study participants will receive up to 3 COVID-19 safety messages. Participants may choose to receive caring messages by text message or paper postcard sent in the mail. Participants with text messages that bounce back to the Johns Hopkins team at any point during the study will be automatically switched to receiving postcard messages until an updated phone number is provided.

ii. Intervention Group ONLY: Caring Contacts est. N = 69

The intervention group will also receive up to 7 culturally responsive caring messages from the research team over a period of three months.

iii. Assessments

During the screening/baseline assessment and all subsequent assessments (30 days $[\pm 10]$, and 90 days $[\pm 10]$ after screening/baseline) all study participants will be contacted to participate in a self-administered survey via REDCap. Paper copies of the questionnaire, along with a scoring manual for study staff to use at baseline for symptom screening), will be available as back-up. This survey will include the mental health measures described below, as well as questions regarding the participants' attitudes and beliefs about COVID-19 prevention strategies (e.g., masking when appropriate, visiting a health care provider), testing, and vaccination. The domains and survey items for

parents/caregivers are listed in Table 5 and the domains and survey items for youth are listed in Table 6 below.

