Analysis for all aims: Are planned statistical analysis will focus on the parent/caregiver surveys, given anticipation that sample sizes will be higher for this group. However, we will analyze the youth self-report descriptively. For adult outcomes, we will examine change over time on outcome measures and differences on these trajectories by study arm (Aim 1) or by timepoint (Aim 2). Additional analyses may also occur depending on guidance from our Community Advisory Boards. Every effort will be made to generate complete data; however, inevitably some data will be missing, and the methods recommended by Schafer and Graham (2002) will be used to evaluate missing data assumptions and guide the analyses. Based on the amount of missing data and evidence for a Missing At Random versus Missing Not At Random missing data mechanism, missingness will be addressed. The missing data approach will be finalized before the outcome analysis. Our analytic plan will also leverage data collected as part of their participation in the Project SafeSchools cohort study (see section XI for details). This will serve as a historical control comparison period for Aim 2, as well as provide a better understanding of longer-term impact of the interventions.

5. Answer the following **if they are relevant to your study design**:

A. If the study has different arms, explain the process for assigning participants (intervention/control, case/control), including the sequence and timing of the assignment.

Participants will be block randomized with blocking on age (e.g., caregiver vs. youth) and gender. A randomization table will be created in a statistical software (e.g., Stata, SAS, R) and incorporated into REDCap. Randomization and assignment of intervention or control groups will occur following consent by a study team member. The study team member will only need to select the randomization option within the participant's study REDCap form for randomization to occur.

B. If human biospecimens (blood, urine, saliva, etc.) will be collected, provide details about who will collect the specimen, the volume (ml) and frequency of collection, how the specimen will be used, stored, identified, and disposed of when the study is over. If specimens will be collected

for use in future research (beyond this study), complete the "Biospecimen Repository" section below.

N/A

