C. If genetic/genomic analyses are planned, address whether the data will be contributed to a GWAS or another large dataset. Address returning unanticipated incidental genetic findings to study participants.

N/A

D. If clinical or laboratory work will be performed at JHU/JHH, provide the JH Biosafety Registration Number.

N/A

E. If you will perform investigational or standard diagnostic laboratory tests using human samples or data, clarify whether the tests are validated and/or the lab is certified (for example is CLIA certified in the U.S.). For clinical tests of human biospecimens, no results may be returned unless completed in a certified lab. Explain the failure rate and under what circumstances you will repeat a test. For all human testing (biomedical, psychological, educational, etc.), clarify your plans for reporting test results to participants and/or to their families or clinicians. Address returning unanticipated incidental findings to study participants.

N/A

- F. If your study involves medical, pharmaceutical, or other therapeutic intervention, provide the following information:
 - a. Will the study staff be blind to participant intervention status?

No blinding will occur.

b. Will participants receive standard care or have current therapy stopped?

Yes, participants will be able to access the current standard of care; participants will be able to access all medical, mental, or behavioral health services they desire. During any study visit, research staff can direct individuals to appropriate sources of information as needed.

c. Will you use a placebo or non-treatment group, and is that justifiable?

The comparison group will receive an evidence-based tool (coping plan + two additional check-in calls or visits) and information on community support services (e.g., tribal behavioral health).

d. Explain when you may remove a participant from the study.

We will not remove any participants from the study.

e. What happens to participants on a study in which there is a medical intervention when the study ends? Will participants continue to have access to the study intervention? What happens if they leave the study early?

N/A

f. Describe the process for referring participants to care outside the study, if needed.

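### The arm is assigned at consent and screening with no blinding, so staff who may know it deliver the coping plan and check-ins that both arms are meant to share equally

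*Combined protocol and SAP*

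**What the plan says.** **Timing of assignment.** Section V.C.1 (Study Implementation) states: "Following consent/assent and screening, participants will be block randomized". Section V.C.5.A, on assignment to arms, states: "Randomization and assignment of intervention or control groups will occur following consent by a study team member". It adds: "The study team member will only need to select the randomization option within the participant's study REDCap form for randomization to occur". Neither section places assignment after the coping plan or the check-ins.

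**Blinding.** The answer to the question on staff blinding in section V.C.5.F.a is "No blinding will occur".

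**Content of the arms.** Section V.C.1 defines the "comparison group (coping plan with two follow-up check-ins" and the "intervention group (coping plan with two follow-up check-ins and culturally adapted Caring Contacts". Apart from the caring messages, the two are the same.

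**Delivery of the shared part.** Under section V.C.1.i, all participants receive a one-hour visit "from a study staff person to develop an individualized plan for coping with life's challenges". A few days later staff call to see how the person is doing and to add referrals. Then: "A second check-in will occur the following week".

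**Schedule.** Table 4 marks the coping plan in M1 Q1, the check-ins in M1 Q1 and Q2, and the first caring message in M1 Q3.

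**The concern.** Hypothesis 1 concerns only what the messages add to coping plans and case management. The comparison isolates that effect if the shared components reach both arms equally. These components leave room for judgement: the plan is individualised, referrals are made as staff see fit, and Table 7 allows 15 to 30 minutes for each check-in. Staff who know that a participant will receive no messages might do more for that person. Staff who favour the new programme might do the reverse. Either response would be mixed with the message effect, and the analysis plan has no variable that could separate them. For adults, the knowledge, access and use of mental health services is also a measured intermediary outcome, and referrals act on it directly.

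The exposure is avoidable, because nothing that the plan describes before M1 Q3 depends on the arm. It also matters beyond this trial: section III.A says that promising results would inform a fully powered study.

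**Working it through.** **1. Does Table 4 support the timing?** The table has three months of four columns, so one column is about 30/4 = 7.5 days. As a check, section V.C.1 sends the COVID-19 messages at about days 45, 60 and 75, and Table 4 marks them in M2 Q3, M3 Q1 and M3 Q3. On the 7.5-day reading those columns start at 30 + 15 = 45, 60, and 60 + 15 = 75. The reading fits. M1 Q3 therefore starts at about day 15, and the shared components fall in about days 0 to 15.

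**2. Are the arms identical until then?** Yes. In Table 4 the arms differ only in the caring-message row, whose first mark is M1 Q3.

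**3. Is the arm hidden in the meantime?** The plan describes no concealment from delivery staff, no separate staff for the shared part, and no comparison of its delivery by arm.

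**4. The plan's own power figure.** Section III.B gives 118 eligible adults, 20% declining and 20% attrition: 118 × 0.8 = 94.4 (94 enrolled) and 94 × 0.8 = 75.2 (75 analysed). With 37.5 per arm, two-sided alpha 0.05 and power 0.80, a two-sample t-test detects d = 0.656, against the stated 0.66. Then 0.66 × 6.4 = 4.2 CESDR-10 points and 0.66 × 5.3 = 3.5 PROMIS points, as in Table 1. The point made here does not alter these figures.

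**5. Illustration of what a shift would do.** The documents give no size for such a shift, so b (in SD) is an assumption. The standard error of the standardised difference is √(2/37.5) = 0.231. If the messages have no effect, the rejection rate is Φ(−1.96 + b/0.231) + Φ(−1.96 − b/0.231).

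| Assumed shift b | CESDR-10 points (6.4 b) | PROMIS points (5.3 b) | Rejection rate, no message effect |
|---|---|---|---|
| 0 | 0 | 0 | 5.0% |
| 0.1 | 0.64 | 0.53 | 7.2% |
| 0.2 | 1.28 | 1.06 | 13.9% |

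The noncentral t with 37 and 38 per arm gives 7.1% and 13.7%.

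A shift in favour of the comparison arm works the other way. At a true effect of 0.66 SD, power is about Φ((0.66 − b)/0.231 − 1.96): Φ(0.90) = 82% at b = 0, Φ(0.46) = 68% at b = 0.1 and Φ(0.03) = 51% at b = 0.2.

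**6. Early leavers.** The plan implies a loss of 94 − 75 = 19 of 94 (20%). If 5 or 10 of these left before the second check-in (an assumption), later randomisation would put the loss after randomisation at 14/89 = 16% or 9/84 = 11%. The number analysed stays at 75, so only the denominator changes.

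**7. Room before the 30-day assessment.** Section V.C.1.iii sets the assessment at 30 ± 10 days after baseline, so its window opens at day 30 − 10 = 20. That is about 20 − 15 = 5 days after M1 Q3 starts.

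**The case against.** **The order is inferred.** No sentence says that randomisation comes before the coping plan, or that the person who randomises also delivers it. This stands as a caveat. Both statements on timing point to consent and screening, however, and with no blinding nothing hides the arm from whoever delivers the plan.

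**Controls exist.** Table 7 sets the same number and length of shared contacts in both arms. Staff are trained on the protocol and the coping plan, with daily site supervision and weekly investigator supervision. Only study management can log in to the text platform (section VI). These measures narrow the scope for unequal delivery. They do not conceal the arm.

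**The bias has no documented size or direction.** This stands in full, and it is why the figures in step 5 are illustration only.

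**Early losses.** A reader might infer that people who leave before the first message dilute the comparison and necessarily lack outcomes. The documents do not support this. The same 75 are analysed under either timing, and people without outcomes do not dilute an analysed contrast. Section XI.A.3 also takes the main Aim 1 outcome from Wave 3 of the parent cohort, so someone who leaves the pilot early may still have it. Nor would later randomisation change non-response at 30 or 90 days.

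**Later randomisation has its own costs.** Baseline would precede randomisation by about two weeks and three support contacts. A late REDCap step could also fall after the 30-day window opens. Both are true, and the second needs an explicit guard. In addition, a pilot of study procedures has an interest in early dropout, so those who leave before randomisation must still be reported.

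**Conclusion.** The point holds as a cheap and worthwhile improvement to Aim 1, not as an error or contradiction in the plan. Assignment is tied to consent and screening, nobody is blinded, and the arms do not differ until about day 15. Staff who may know the arm therefore deliver shared components that involve judgement. The result is an avoidable risk of performance bias, of unknown size and in either direction.

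The rise from 5% to about 7% to 14% rests wholly on an assumed shift of 0.1 to 0.2 SD and on a two-sample comparison of 75 adults. The lower post-randomisation loss in step 6 is likewise illustrative. A reader might go further and conclude that delivery will be unequal, or that the Aim 1 result would be invalid. The documents show only that unequal delivery is possible and that the arm is not hidden.

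The within-subject comparison in Aim 2 does not depend on the arm. Unblinded outcome assessment, including staff reading questions aloud by phone, is a separate matter that this change does not address.

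**What to change.** Amend sections V.C.1 and V.C.5.A in one of two ways:

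- **Randomise later.** Run the REDCap randomisation at a fixed time after the second check-in is due and just before the first caring message.
- **Reveal later.** If randomisation stays at consent, keep the assignment hidden from the staff who deliver the coping plan and check-ins until that same time.

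Under later randomisation, include everyone still enrolled, whether or not the check-ins were completed, so that the randomised group is not selected on adherence. Under either option, state that the step always takes place before day 20, when the 30-day window opens. Keep baseline and the 30- and 90-day anchors as they are, and show people who leave before randomisation in the participant flow.

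**Cost.** No extra visits or staff, and no change to what participants receive. With later randomisation, a few enrolled people may never be randomised, baseline precedes randomisation by about two weeks, and REDCap needs an action at a later date. Revealing later leaves the randomised group as now planned, but requires control over who can see the assignment until the second check-in has passed.
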